Using 30 healthy cannabis users (15 men, 15 women), this study will be one of the first to assess changes in eye behavior as a function of recent cannabis use within a quantified virtual reality (VR) environment. We will examine the effect of smoked cannabis (7% vs. 0% THC) on individual eye movements, with the goal of defining the utility of the eyes as potential objective indicators of cannabis use and intoxication. Four eye tests (nystagmus, smooth pursuit, convergence, and pupillary light response; outlined below), which previous literature has defined as effective in detecting recent drug use (including opioids and alcohol; Murillo et al. 2004), have been compiled into a 5-minute task battery using a VR headset environment equipped with high frequency infrared eye trackers (the HTC Vive with Pupil Labs Tracking). This 5-minute VR battery of four eye tests will be administered prior to cannabis consumption as a baseline, and then at 0, 15, 30, 45, 60, 75, 90, 105, 120, and 165 min after cannabis, with the goal of comparing baseline values to the ten post-cannabis timepoints to detect changes in eye behavior as a function of cannabis intoxication. We will also administer a battery of subjective-effects and mood visual analogue scales (0-100 mm; e.g. 'Good Drug Effect') prior to the eye test battery at each timepoint, allowing us to correlate each outcome of the eye tasks to subjectively reported cannabis impairment and mood.

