- 1) Smooth pursuit: This refers to the eyes' ability to fixate on and track a moving target smoothly, without saccades (Hartman et al. 2016). Some studies indicate that smooth eye pursuit may vary as a function of cannabis use, with chronic users displaying less of a deficit in this task vs. less habitual users (Firth, 2006). Central nervous system depressants and cannabis significantly increase the chance of lack of smooth pursuit and distinct nystagmus at maximum deviation (Porath-Waller et al. 2013). This study will measure the number of saccadic eye movements as the stimulus moves across the screen.
- 2) Nystagmus (horizontal, vertical, resting): This characteristic is an involuntary jerking of the eye, and is a common effect of many drugs of abuse including cannabis, but also opioids and barbiturates (Peragallo et al. 2013). Tests of nystagmus tend to correlate with impairment. Nystagmus at maximum deviation occurs when a participant is able to hold their eyes steady on a non-moving target without a nystagmus (Hartman et al. 2016). In this study, the stimulus will appear at the edges of the visual field both

horizontally and vertically, referred to as HGN and VGN respectively. We will assess the number and amplitude of jerky eye movements when the stimulus is at an extreme.

- 3) Convergence: This refers to the eyes' ability to converge, or cross, while a participant focuses on a target that is moved slowly towards the bridge of their nose (Hartman et al. 2016). If a participant is unable to converge on a target a minimum of 2 inches from the bridge of the nose, lack of convergence is established and considered to be a sign of impairment (Stapleton et al. 1986). This study will measure maximum binocular adduction (both pupils moving inward) to quantify participants' ability to converge.

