- 4) Pupil dilation: Pupillary Light Reflex (PLR): In this test, the eye tracking environment will go from dark to bright light instantly and pupil size will be tracked. There is some controversy about the impact of cannabis on pupil diameter, hence the need for further research to characterize the relationship between cannabis intoxication and pupil diameter. Some studies have shown pupil constriction (miosis), some have shown no change in pupillary size, and some have reported dilated pupils (Bramness et al., 2010). Yet, the majority of research shows some relationship between cannabis intoxication and pupil dilation. Pupillary reaction to light tends to be slow when a participant is under the influence of cannabis within the first few hours following consumption (Bramness et al., 2010), suggesting a potential method of testing recent cannabis use amongst drivers. Rebound dilation has been shown to be related to cannabis use in a study in which the pupil diameter at the end of the presentation of a bright stimulus was significantly affected by cannabis (Fant et al. 1998).

In this study, the following latent features related to pupil behavior (not directly observable but calculated later in a Principal Component Analysis and Factor Analysis) will also be analyzed:

1. Rebound dilation: a period of pupillary constriction that is immediately succeeded by a period of pupillary dilation. The light level tests allow for the assessment of rebound dilation when the lights engage, as the pupils constrict in response.
2. Maximum constriction velocity (MCV): a measure of the most extreme rate of change in pupil size during a constriction event. These data are collected during the light level tests as the pupils constrict in response to the light's engagement.
3. Response Latency: the time it takes for the pupil to begin constricting after the light stimulus is turned on. Response latency refers to the biological lag in the pupillary light reflex.
4. Max/Min Pupil Size: Miosis (1.5-2mm)/Mydriasis (7.5-8mm)

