State of the field and current limitations: Previous research on the effects of cannabis on the eyes has been conducted, yet most of this research is decades old and used outdated technology that cannot accurately or frequently measure eye movements and pupil dilation. The literature also presents contradicting results on correlations between cannabis and certain eye movements, specifically regarding nystagmus and smooth pursuit. Despite these studies and the fact that eye movements are currently used in the field to detect drug intoxication, little is known about the causal relationship, if any, between cannabis, eye movements and pupil dilation. To date, no published studies have used modern VR eye trackers and data analysis to build a predictive model of cannabis intoxication. The current study seeks to explore the effects of cannabis on eye movements using a sophisticated eye tracking software to provide an objective, accurate measure of cannabis impairment.

Specific Aims and Hypotheses

Aim 1: Examine the relationship between cannabis intoxication and eye behavior.

Hypotheses: (a) Active cannabis (7% THC) will have an effect on eye behavior, evidenced by lack of convergence, lack of smooth pursuit, presence of nystagmus and pupil dilation when compared to inactive placebo cannabis (0% THC).

Exploratory Aim: Examine the relationship between experimental pain and pupil size.

Hypotheses: (a) Changes in pupil size will correlate with subjective reports of experimental pain threshold and tolerance using Quantitative Sensory Testing thermal pain.

Inclusion/Exclusion Criteria

Description of Subject Population:
Non-treatment seeking cannabis smokers.

CRITERION	METHOD OF ASCERTAINMENT
Inclusion:	
1. Males/non-pregnant females aged 21-55 years	Age verified via identification/Non-pregnancy confirmed via urine toxicology
2. Report smoking cannabis \geq 1 day per week, and \geq 1 joint (~0.5 grams) per smoking day, during the 4 weeks prior to screening	Self-report during clinical interview
3. Urine test positive for recent cannabis use	Urine toxicology
4. Body Mass Index from 18.5-34 kg/m ²	Physical examination
5. Not currently seeking treatment for their cannabis use	Self-report during clinical interview
6. Able to perform all study procedures (i.e., does not experience discomfort or nausea from VR headset, can perform computer tasks)	Training session

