7. For women, not pregnant, lactating, or breast-feeding and currently practicing an effective form of birth control (double-barrier methods, hormonal birth control pills, hormonal implants, or IUDs)	Self-report during clinical interview, blood, and urine pregnancy test (7091R), physical examination
Exclusion:	
1. Meeting the DSM-V criteria for Severe Cannabis Use Disorder or any other Use Disorder other than for Cannabis, Nicotine, or Caffeine; any other psychiatric disorder	Clinical interview
2. Report using other illicit drugs \geq 1 day/week in the prior 4 weeks; positive for anything other than THC > 1x during screening	Clinical interview, urine toxicology
3. Abnormality with the eyes which may affect the eye tracking technology such	Physical examination, training/calibration session with VR eye-tracking device

as color blindness, naturally occurring nystagmus, amblyopia, strabismus, age-related macular degeneration (AMD), cataract, diabetic eye disease, glaucoma, dry eye, extreme refractive error, bacterial or viral infections of the eye.	
4. If medical history, physical and psychiatric examination, or laboratory tests performed during the screening process revealed any significant illness (e.g., diabetes, cardiovascular disease, hypertension (BP >140/90), hepatitis, clinically significant laboratory abnormalities, chronic obstructive pulmonary disease, Parkinson's disease, dementia, cognitive impairment, history of a seizure disorder, history of traumatic brain injury, any immunocompromising conditions such as HIV/AIDS, cancer, or diabetes, or LFTs > 3x upper limit of normal)	Medical history, physical examination, laboratory tests, ECG
5. Current licit use of medical cannabis	Self-report, physical examination
6. Current pain	Self-report during clinical interview, physical examination, medical history
7. User of supplemental oxygen	Medical history, physical examination

Study Procedures

General Overview

This study will examine the effects of cannabis intoxication on eye behavior. Eleven eye-task batteries will be conducted with a VR HTC Vive with Pupil Labs Eye Tracking headset. Healthy cannabis users (N=30, 15M, 15F) will complete a training session followed by two counterbalanced outpatient laboratory sessions in a randomized, double-blind, placebo-controlled (0% vs. 7% THC) design.

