In each session, the participant will smoke two-thirds of one cannabis cigarette according to our paced-puff procedure (Foltin et al. 1987). They will complete an eye task battery (5 minutes per battery) 15 minutes prior to smoking as a baseline measure in each session, and again at the following timepoints: 0, 15, 30, 45, 60, 75, 90, 105, 120, and 165 minutes post-cannabis. Baseline assessments will be compared to those at post-cannabis timepoints.

In order to collect exploratory data, we will also conduct one pain assessment during the training session (described below).

Screening:

Initial telephone interviews will be carried out by research assistants who have been trained by [name], during which time potential participants will be asked about their current and past drug use and general health. To conduct this telephone interview, we are requesting a waiver of consent.

After initial determinations of eligibility over the phone, volunteers will come into the Cannabis Laboratory for two screening visits. At the first screening visit, they will be asked to sign our currently approved outpatient screening consent form (#7091R), allowing us to collect questionnaire data, conduct interviews, obtain medical information including a medical history and bloodwork (including blood pregnancy test for women at screening), and do an ECG. Potential participants will be told that they will be taking part in a study investigating the effects of smoked cannabis and eye movements. After the general screening process, a study psychologist ([name], [name], [name]) will explain the details of the study procedure and confirm that the volunteer understands what participation entails, after which they will sign the study-specific consent form (#7844).

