Participants will arrive at NYSPI at 9 am and be given a light breakfast. Vitals (blood pressure/heart rate) will be performed prior to initiating each session. Participants will complete two baseline eye-tracking batteries prior to cannabis administration at each of the two sessions (7% or 0%). Participants will be seated and asked to wear a VR headset connected to the host PC. The headset will be placed on the participant's head and the tracker will be calibrated in a standard calibration. A research assistant may help the participant adjust the headset so that their pupils are centered, and so that the headset is securely placed on their head.

The 5-minute battery of four eye tasks will be administered through the VR headset at 0, 15, 30, 45, 60, 75, 90, 105, 120, and 165 mins after cannabis smoking over the time course of cannabis intoxication. Before each eye test, there will be a calibration which takes between one to three minutes. Vitals (heart rate, blood pressure) will be measured at the end of each of these timepoints throughout the session.

Prior to each eye test at 0, 15, 30, 45, 60, 75, 90, 105, 120, and 165 minutes post-cannabis, the participant will also complete a 3-minute subjective-effects battery, consisting of a series of VAS in which participants indicate how they are feeling at that moment. The 44-item VAS includes mood, physical symptom and drug effect descriptors. Based on a cluster analysis, we employed arithmetic means of individual item scores to reduce 34 of the 44 items into eight subscales: good drug effect; miserable; irritable; anxious; bad effect; social and confused. We also analyze individual VAS drug craving ratings. These subjective measures may detect changes in abuse-related effects as well as changes in mood (miserable, irritable, anxious, cannabis craving) as a function of cannabis condition, and will be correlated to changes in the eye-tracking battery.

The order of the eye tests within the battery will be standardized and will not change across timepoints or sessions. The eye tests are conducted in a VR environment where a fixation point (target) in the shape of a cross – the stimulus – is virtually projected 12 inches in front of the participant. The participant will be asked to follow the center of the target without moving their head. The fixation point's movements are based upon the tests below:

1. Nystagmus:

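### Aim 1 and the design call for a 7% versus 0% THC comparison of eye outcomes, but the only comparison written down is baseline versus post-smoking

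*Combined protocol and SAP*

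**What the plan says.** **Goal and design.** The Lay Summary gives the goal as the effect of 7% versus 0% THC on eye behaviour. Specific Aims and Hypotheses repeats it: Aim 1 predicts changes in convergence and smooth pursuit, together with "presence of nystagmus and pupil dilation when compared to inactive placebo cannabis (0% THC". Study Procedures, General Overview, describes 30 participants and two counterbalanced sessions "in a randomized, double-blind, placebo-controlled (0% vs. 7% THC) design".

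**Comparison of eye values.** Two sentences say which values are set against which. The Lay Summary describes repeating the battery "with the goal of comparing baseline values to the ten post-cannabis timepoints to detect changes in eye behavior as a function of cannabis intoxication". General Overview, directly after the assessment times, says "Baseline assessments will be compared to those at post-cannabis timepoints".

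**Other analyses named for the eye data.** Latent pupil features are to be "calculated later in a Principal Component Analysis and Factor Analysis" (A Proposed Objective Ocular Approach). Under Laboratory Sessions, the subjective ratings may show changes "as a function of cannabis condition, and will be correlated to changes in the eye-tracking battery".

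**Outcomes.** The same Ocular Approach section lists several measures without ranking them. Examples are "This study will measure the number of saccadic eye movements as the stimulus moves across the screen" and, for nystagmus, "We will assess the number and amplitude of jerky eye movements when the stimulus is at an extreme". The document has no statistical analysis section, model, alpha, multiplicity rule or period term.

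**The concern.** The placebo session is there to remove whatever happens to the eyes over roughly three hours of repeated testing regardless of THC: fatigue, repeated bright-light and dark phases, and the act of smoking. A baseline-versus-post comparison within a session does not use it. An analyst who follows the two written sentences could report a change after 7% THC as a cannabis effect, or argue from significance in one session and not the other, without ever testing dose. Either route can produce an effect from shared drift, and the second can also hide a real one. The opening for selection is wide, with several eye measures, ten post-smoking timepoints and more than one description of the baseline.

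**Working it through.** **1. Does any other statement supply the dose test?** No.
- The statements of goal, hypothesis and design name 7% versus 0% THC but give no procedure.
- Component and factor analysis reduce the pupil data; they do not compare doses.
- In Laboratory Sessions, cannabis condition is attached to the subjective ratings. The eye battery enters only as something correlated with them.

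**2. Inputs.** n = 30 is from General Overview. The plan has no figure to reproduce: it gives no SD, alpha, effect size or sample-size calculation. Everything else is assumed: two-sided 5%, one outcome at one timepoint, all 30 complete, no period effect, no carryover. Let D7 and D0 be the changes from baseline in the 7% and 0% sessions, each with SD 1 and correlation r. With no THC effect, both have mean d, the shared drift in SDs of the change score.

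**3. Error rates with no THC effect.**
- *7% session alone:* one-sample t test, 29 df, critical value 2.045, noncentrality d × √30. Call the rejection probability p.
- *Sessions judged separately (7% significant, 0% not):* p(1 − p) if r = 0; by simulation (40,000 runs) if r = 0.5.
- *Direct contrast:* paired test of D7 − D0, whose mean is d − d = 0.

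| d | d × √30 | 7% alone, p | p(1 − p), r = 0 | separate, r = 0.5 | direct contrast |
|---|---|---|---|---|---|
| 0.2 | 1.095 | 0.185 | 0.151 | 0.11 | about 0.05 |
| 0.3 | 1.643 | 0.355 | 0.229 | 0.16 | about 0.05 |
| 0.5 | 2.739 | 0.754 | 0.185 | 0.13 | about 0.05 |

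Simulated rates for the direct contrast were 4.8% to 5.2%.

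**4. Missed effects.** Judging sessions separately produces fewer false positives at large drift only because both sessions become significant. At d = 0.8, p = 0.988 and p(1 − p) = 0.011. With a true THC effect of 0.8 SD and drift of 0.5, the 7% session is almost always significant, so the separate-session rule shows the effect in about 1 − 0.754 = 0.246 (25%). The direct contrast has SD √(2(1 − r)). For r = 0 its standardised effect is 0.8/1.414 = 0.566, with power 85%. For r = 0.5 it is 0.8, with power 99%.

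**5. What the direct contrast costs.** Take a true effect of 0.5 SD and no drift.
- r = 0: separate-session rule 0.754 × 0.95 = 0.716. Contrast 0.5/1.414 = 0.354, noncentrality 1.936, power 0.465.
- r = 0.5: rule about 0.72 (simulated), contrast 0.754.

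**6. Adjusted version.** Steps 3 to 5 use a simple paired contrast of change scores. A paired 7%-minus-0% window mean, adjusted for baseline difference and sequence, was simulated separately. That model assumed between-person SD 1, between-session SD 0.3 and residual SD 0.5, with drift and period effects from 0 to 0.5 in those raw units. Its false-positive rate was 4.3% to 5.7%.

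**7. Multiplicity remains.** The Ocular Approach section yields about eight eye measures: saccade number, nystagmus number and amplitude, maximum adduction, rebound dilation, constriction velocity, latency and pupil size extremes. Eight unadjusted independent dose tests at one timepoint give 1 − 0.95^8 = 0.337. At correlations of 0.5 and 0.8 the simulated figures are 25% and 16%.

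**8. Which baseline?** General Overview has one battery 15 minutes before smoking and speaks of eleven batteries, which fits 1 + 10 = 11 per session. The session schedule has one baseline slot at −30 minutes. Laboratory Sessions reads as two baseline batteries per session, which would make 2 + 10 = 12.

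**The case against.** The best reply is that the dose comparison is plainly intended. The Lay Summary states it for the eye data, Aim 1 repeats it, and the General Overview sentence follows a list of assessment times, so it may only explain why each session has a baseline. Nothing confines the comparison to one session. This stands as far as intent goes. A reader might infer that the investigators have chosen the wrong comparison or will not compare the doses; the documents support neither. The finding is that the test of dose is not specified.

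A reader might also infer that the plan will declare an effect when the 7% session is significant and the 0% session is not. No section states that rule. It is used here only to show what separate within-session testing can do.

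Other points partly stand. The drift values are assumed. Training Session 1 gives at least 10 minutes in an identical virtual environment, which should reduce practice effects, though not fatigue, light exposure or the effect of smoking. The study describes itself as exploring effects and seeking a pattern, so insisting on a single primary outcome is partly a matter of preference. The count of eight measures includes pupil features to be derived by component and factor analysis. Finally, Laboratory Sessions allows the two sessions to follow with no wash-out, so the direct contrast has an assumption of its own.

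**Conclusion.** The concern holds as a gap in specification that should be fixed. The plan's goal, hypothesis and design all point to 7% versus 0% THC, while its only written comparison of eye values is baseline versus post-smoking, which does not answer Aim 1 on its own.

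Under the assumptions in the working, a shared drift of 0.2 to 0.5 SD of the change score makes the 7% session significant in 19% to 75% of trials with no THC effect. Those figures are an upper illustration and should not be read as this trial's error rate, because nothing says the placebo session is ignored. Judging the sessions separately gives 15%, 23% and 19% (uncorrelated changes) or 11%, 16% and 13% (correlation 0.5). The direct contrast stays near 5%. That last result requires drift to be equal in the two sessions and no carryover beyond what each session's baseline captures.

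The conclusion that dose is untested as written rests on the text and does not depend on the drift values.

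**What to change.** Replace the comparison sentence in General Overview with: *Post-smoking eye values will be compared between the 7% and 0% THC sessions within participant, adjusted for each session's pre-smoking baseline and for session period; change from baseline within a session is descriptive.* Align the Lay Summary clause to the same baseline-adjusted between-dose comparison, so that the plan names one estimator.

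Also:
- Before unblinding, state how multiplicity across the eye outcomes and ten timepoints is handled, for example Holm across named outcomes on a pre-named post-smoking summary. The choice of outcomes and window is the sponsor's.
- Acknowledge that sessions may run with no wash-out and that the contrast therefore assumes no carryover beyond what the session baseline captures.
- Reconcile the number and timing of baseline batteries across General Overview, Laboratory Sessions and the session schedule. If there are two, say how they are combined.

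**Cost.** One sentence, one clause, a short statement on multiplicity and some added analysis; no new data, visits or participants. The real price is noise from two sessions. With no drift and uncorrelated changes, a 0.5 SD effect is found in 46.5% against 71.6% for separate within-session testing. At correlation 0.5 the figures are about 75% against 72%, so the loss disappears.
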